### **8.4 Inclusion/Exclusion Criteria**

Inclusion and exclusion criteria deviations will be provided in a data listing by subject.

### **8.5 Demographic Characteristics**

Subject demographics at screening: gender; age; ethnicity; height; weight; and, race, will be summarized by treatment cohort and overall.

Gender, ethnicity, and race will be summarized as the number and percentage (n, %) of subjects within each category by treatment cohort and overall. Denominators used in the calculation of percentages will be based on the number of subjects in the analysis population for each treatment cohort and overall.

Age, weight, and height will be summarized as a continuous variable using descriptive statistics (n, mean, standard deviation, median, minimum, and maximum) by treatment cohort and overall.

Demographic characteristics will be provided in a data listing by subject.

### **8.6 Clinical Stage**

Subject clinical stage at study entry will be summarized by diagnosis type (Lymphoma or Solid Tumor). For subjects with Lymphoma diagnosis, the summary of clinical stage will include stratification on the following factors: FDG avidity status; Lymphoma type; and, Lugano Stage at study entry. For subjects with Solid Tumor diagnosis, clinical stage will be summarized by TNM Stage at study entry. Summaries will present the number and percentage of subjects by treatment cohort and overall. Denominators used in the calculation of percentages will be based on the number of subjects in the analysis population for each treatment cohort and overall.

Clinical stage will be presented in a data listing by subject.

## **8.7 Prior Antineoplastic Therapy**

Prior antineoplastic cancer therapy will be reported in a data listing by subject.

## **8.8 Medical History**

Medical history (excluding prior antineoplastic cancer therapy) will be provided in a data listing by subject.

# **9 EFFICACY ANALYSIS**

The PP population and EP will be used for summaries and analyses of the efficacy variables described below.

All efficacy results for each lymphoma type will be calculated and presented separately. Efficacy results for solid tumor patients will be shown in listings, and parameters will be shown in text and text tables by range only.

If Part B is not completed for at least one indication, efficacy parameters will only be reported as individual patient listings for summary descriptive reporting in the CSR.

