**Statistical methods:**

**Analysis Populations:**

The safety population will include all subjects who take at least 1 dose of study medication. Safety analyses will be conducted using the safety population. The safety population will apply to Parts A and B.

The PK population will include all subjects who receive at least 1 dose of ASN002 and have sufficient plasma concentration data to facilitate the calculation of PK parameters.

The PD population will include all subjects who have a baseline and a post dose assessment of the PD parameters, where a change from baseline is determined.

The Efficacy Population (EP) will include all subjects who have an evaluable screening and post-dose tumor assessment.

The Per Protocol (PP) population will include all EP subjects without major protocol violations. The PP population will be used as the primary analysis population for efficacy.

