### 5.2 Efficacy Population (EP)

The efficacy population (EP) will include all subjects who have an evaluable screening and post-dose tumor assessment. The EP will be used as the supportive analysis population for summaries and analyses of the efficacy endpoints. No EP will be reflected if Part B is not completed for at least one indication.

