### 5.3 Per-Protocol (PP) Population

The PP population includes all EP subjects without major protocol deviations. The PP population will be used as the primary analysis population for efficacy summaries and analyses. No PP will be reflected if Part B is not completed for at least one indication.

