### **9.2 Evaluation of Time to Treatment**

The time (days) on treatment, beginning with the date of first administration of study drug and ending with the date of discontinuation or completion of study treatment, will be provided by treatment cohort using descriptive statistics (n, mean, standard deviation, median, minimum, and maximum).

Time on treatment will be provided in a data listing by subject.

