#### **9.5 Exploratory Efficacy Variables**

##### **9.5.1 Panel of Biomarkers**

Serum concentrations of the biomarkers Phospho-S6, Phospho-STAT3, Phospho-SYK 525/526, Phospho-ERK, basal B-cell surface activation markers, CD69, CD88, and the panel of markers of inflammation (see Appendix C of the Study Protocol), including CRP,  $\beta$ 2-microglobulin, and IL-10, will be collected pre-dose on Day 1 of Cycle 1 (baseline assessment) and at the visits/timepoints indicated within the within the Schedule of Assessments (see [Section 3.2](#)). For each biomarker and post-baseline assessment, change from baseline (CFB) in the biomarker will be calculated as the difference between the post-dose assessment and the baseline value (i.e., CFB in biomarker = post-dose biomarker value – baseline biomarker value).

Summaries for absolute and CFB for each biomarker will be provided by visit/timepoint and treatment cohort using descriptive statistics (n, mean, standard deviation, median, coefficient of variance, minimum, and maximum).

Absolute and CFB for each biomarker will be provided in a data listing by subject.

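### SAP Section 9 ties the biomarker summaries to subjects with a post-dose tumor assessment, instead of using the PD population defined in the protocol synopsis

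*SAP*

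**What the plan says.** SAP Section 9 sets one rule for everything beneath it: "The PP population and EP will be used for summaries and analyses of the efficacy variables described below". SAP 5.2 defines the first of these sets: "The efficacy population (EP) will include all subjects who have an evaluable screening and post-dose tumor assessment". SAP 5.3 makes the other a subset of it: "The PP population includes all EP subjects without major protocol deviations". Both sections add a contingency, worded in 5.3 as "No PP will be reflected if Part B is not completed for at least one indication".

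The biomarkers come under this rule. SAP 2.3.1.3 lists them as exploratory efficacy variables, and SAP 9.5.1 states: "Summaries for absolute and CFB for each biomarker will be provided by visit/timepoint and treatment cohort". It names no population. It also provides a by-subject listing.

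The protocol synopsis, under Analysis Populations, has a separate set: "The PD population will include all subjects who have a baseline and a post dose assessment of the PD parameters". It asks for no tumor assessment. Protocol 15.2 does not repeat this definition, and Protocol 15.8 promises descriptive PD statistics by dose level without naming a population. SAP Section 5 contains only the Safety, EP and PP sets. SAP Section 14 says nothing was changed from the protocol, and Protocol Section 15 gives the SAP priority where the two differ.

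**The concern.** Being in the EP depends on being scanned after dosing, and a biomarker change from baseline does not need that. A subject can have a full set of PD samples and still be left out of the PD tables because no evaluable scan followed. Such subjects are unlikely to be a random sample. They include those who die, refuse final procedures, or stop on clinical progression without imaging, and these reasons may be related to dose. Part A dose levels hold three to six subjects, so one exclusion changes a cohort mean noticeably.

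The PD objective covers Parts A and B. Under the present wording, whether Part A biomarkers are summarized at all could also depend on whether a Part B indication completes, which has no bearing on the Part A PD data.

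**Working it through.** **1. Governing population.** The Section 9 rule covers 9.5.1, and 9.5.1 does not override it. The EP takes in "all subjects who have an evaluable screening and post-dose tumor assessment"; the PP set also removes major deviators. The synopsis PD set needs a PD pair only. A subject with a PD pair and no evaluable post-dose scan is therefore in the PD population but in neither the EP nor the PP set.

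**2. Timing.** In Part A, PD samples are taken on Day 1 (predose and 2 hours), Day 8, Day 15 and Cycle 2 Day 1 (Table 3 of both documents).
- Last PD sample: after one 28-day cycle, so week 4.
- First scheduled scan, solid tumors: 2 × 28 = 56 days, so week 8 (SAP 9.1.1).
- First scheduled scan, lymphoma: 3 × 28 = 84 days, so week 12 (SAP 9.1.1).
- Gap: 8 − 4 = 4 weeks or 12 − 4 = 8 weeks, one week less if the scan uses the permitted early window.

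**3. Who is lost.** Protocol 10.4 requires a disease assessment within a week of the last dose, and 9.3 applies the end-of-treatment procedures to anyone who discontinues. Stopping inside the gap therefore does not by itself remove a subject. Removal needs a missed or non-evaluable final assessment as well. SAP 10.1 expects some such cases, since it plans a listing of subjects who drop out for adverse events before any post-dose tumor assessment.

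**4. Size.** The plan gives no figure for this group. The nearest is the 10% early-termination allowance in Protocol 8.2, which reproduces: 148 × 1.10 = 162.8, about 163. (Dividing instead, 148 / 0.90 = 164.4, gives 165.) That is a rate of stopping early, not of lacking a scan. Protocol 6.3 reports 21 of 27 discontinued, 13 for progression, leaving 21 − 13 = 8 (8/27 = 30%) for other reasons. It does not say how many had no post-dose scan.

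Per subject lost: 1/6 = 17% of a six-subject cohort and 1/3 = 33% of a three-subject cohort.

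As an assumption only, let a share d of subjects have PD pairs but no evaluable post-dose scan, independently of one another:

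| d | Expected in Part A (64 × d) | Chance that a cohort of 6 loses at least one, 1 − (1 − d)^6 |
|---|---|---|
| 5% | 3.2 | 27% |
| 10% | 6.4 | 47% |
| 30% | 19.2 | 88% |

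The 30% row would need every non-progression discontinuation to lack a scan. The required end-of-treatment assessment argues for a much smaller share.

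**5. Part B contingency.** If no indication completes, SAP 5.2 and 5.3 withhold both sets, and Section 9 reduces efficacy parameters to individual listings. SAP 9.5.1 promises cohort summaries with no such condition, and so does Protocol 15.8. Applied literally, the Section 9 rule leaves those summaries with no population.

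**6. Time on treatment.** SAP 9.2 summarizes "The time (days) on treatment, beginning with the date of first administration of study drug" under the same rule. SAP 10.2 summarizes duration of exposure, from first to last dose, in the Safety Population. Two nearly identical durations would be reported in different sets.

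**The case against.** The strongest reply is that the gap closes itself when the protocol is followed. A subject who stops in week 5 should have an end-of-treatment disease assessment and can enter the EP. This is right, and it limits the loss to subjects whose final assessment fails. It does not supply a reason for the restriction.

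Second, the PD population appears only in the synopsis, so the inconsistency starts in the protocol. That also stands, and it means the protocol needs correcting as well as the SAP. It does not show that anyone chose the EP or PP set for PD.

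Third, the by-subject listings remain, so no data disappear. That is true: the loss is from the summary tables. SAP 11.2 defers PK and population PK/PD modelling to other plans, but it does not defer the 9.5.1 tables.

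A reader might go on to infer two stronger things that the documents do not support. One is that the biomarker selection affects the Part B dose. Protocol 6.4.3 records that the safety review committee had already agreed that dose, citing toxicity findings; biomarker inhibition is an additional observation. The other is that reported time on treatment will be materially biased upward. The documents give no distribution of stopping times from which to size such a bias, the required final assessment would weaken it, and SAP 10.2 gives nearly the same quantity without the selection. The protocol also places time on treatment under efficacy, so the SAP does not depart from it there.

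**Conclusion.** The rule is wrong as written for the biomarkers. It conditions an exploratory PD summary on a tumor assessment that the summary does not need, it departs from the synopsis, and the departure is undeclared. The effect is on descriptive tables only; no hypothesis test is involved. The size cannot be determined from the documents. It is 17% of a six-subject cohort for each affected subject, and the number affected depends on how often end-of-treatment assessments are missed or not evaluable. The Part B contingency is the larger exposure: read literally, all Part A biomarker summaries would become listings, contrary to Protocol 15.8. That reading depends on letting the opening of Section 9 override the unconditional wording of 9.5.1, and the SAP does not settle which prevails. The time-on-treatment placement is a minor consistency point.

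**What to change.** - Add the synopsis PD population to SAP Section 5 and to Protocol 15.2, so that all three places agree.
- Name it in SAP 9.5.1 as the population for the biomarker summaries, whether or not any Part B indication completes.
- Reword the opening of SAP Section 9 so that the EP and PP sets, and the listings-only contingency, apply only to endpoints that need a disease assessment.
- For consistency, report time on treatment (SAP 9.2) in the Safety Population, as 10.2 already does for duration of exposure.
- Until the protocol text is aligned, record the difference in SAP Section 14.

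The cost is wording in two documents and revised table shells. No new data are needed.

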## **9.1 Evaluation of Disease Status**

### **9.1.1 DLBCL, MCL, FL, PTCL**

For cohorts that have at least 5 subjects at the recommended Part B dose of 75 mg BID, the frequency of responders according to the 2014 Lugano Classification for subjects with lymphoma will be evaluated at each dose level and for each lymphoma subgroup in Part B. Differences in response to therapy based on the molecular subtypes of DLBCL will be explored.

Assessments will be made after every two 28-day cycles of therapy, i.e., starting just before Day 1 of cycle 3 and then just before each odd-numbered cycle, for solid tumor patients and after every 3 cycles, i.e., just before Day 1 of cycle 4 and then just before cycles 7, 10, and 13, etc, for lymphoma patients.

In Part B, response to treatment will be analyzed using the binomial test for each of the disease-specific cohorts (DLBCL, MCL, FL, PTCL, MF and CLL). The dichotomous classifications to be assessed in each binomial test are disease responders versus non-responders. Responders will be considered as subjects with 2014 Lugano Classifications given by Complete Response (CR) or Partial Response (PR), and non-responders as subjects with 2014 Lugano Classifications given by No Response (NR) or Stable Disease (SD), or Progressive Disease (PD). For each binomial test, the null hypothesis is that the rate of disease responders is 5% and the one-sided alternative hypothesis is that the rate of disease responders is greater than 5%. The null hypothesis will be rejected if the p-value is less than 0.05 (i.e., using a one-sided significance level of 0.05).

Summaries for best disease response will be provided by treatment cohort for subjects diagnosed with lymphoma using frequencies (counts and percentages). For Part B, the estimated rate of disease responder and the p-value from the binomial test will be provided by disease-specific cohort (DLBCL, MCL, FL, PTCL, MF and CLL).

Response to treatment will be provided in a data listing by subject.

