**Efficacy Analyses:**

Evaluation of response rate and survival rate: Responses will be listed by tumor type and dose level.

In Part B, the overall response rate (ORR), time to progression (TTP) and progression free survival (PFS) will be reported for each lymphoma histology, MF, and CLL.

Evaluation of time on treatment: The time from the start of study treatment to the discontinuation or completion of study treatment at each dose level will be summarized descriptively.

All efficacy summaries will be performed by dose level and Parts A and B, separately and combined, if appropriate.

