#### **DLBCL, MCL, FL, and PTCL**

The International Conference on Malignant Lymphoma (ICML) Recommendations for Initial Evaluation, Staging, and Response Assessment of Hodgkin and Non-Hodgkin Lymphoma (2014 Lugano Classification) will be used to determine the stage of subjects with lymphoma, and the response to treatment.

For cohorts that have at least 5 subjects at the recommended Part B dose of 75 mg BID, the following endpoints will be used to determine the response to treatment with ASN002 in subjects with lymphomas:

- Objective Response Rate
- Duration of Response
- Time to Tumor Progression (TTP)
- Progression-free Survival (PFS)
- PFS rate at week 24

For cohorts with less than 5 subjects at the recommended Part B dose of 75 mg BID, efficacy will be summarized in a descriptive manner for those subjects who have at least stable disease per protocol criteria.

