### **Myelofibrosis**

The International Working Group-Myeloproliferative Neoplasms Research and Treatment (IWG-MRT) and European LeukemiaNet (ELN) response criteria will be used to evaluate the response to treatment with ASN002. If less than 5 subjects were enrolled at the recommended Part B dose of 75 mg BID, efficacy will be summarized in a descriptive manner for those subjects who have at least stable disease per protocol criteria.

The following endpoints will be used to determine the response to treatment with ASN002 in subjects with MF:

- Splenic response rate at week 24
- Clinical improvement rate at week 24
- Symptom response evaluated using the Myeloproliferative Neoplasm Symptom Assessment Form (MPN-SAF) tool
- rate of RBC transfusion through week 24

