### **9.1.3 Myelofibrosis**

For cohorts that have at least 5 subjects at the recommended Part B dose of 75 mg BID, the frequency of response and type of response according to IWG-MRT response criteria for subjects with MF will be evaluated. The frequency of disease assessment to treatment and type of response (e.g. every 2 months, and spleen volume) will be provided in a data listing by subject.

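### SAP 9.1.1 writes a Lugano-only responder rule for binomial tests in all six Part B cohorts; it does not fit MF or CLL, and for MF no responder is defined for the test.

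*SAP*

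**What the plan says.** SAP 9.1.1, headed for the four lymphomas, states that Part B response will be "analyzed using the binomial test for each of the disease-specific cohorts (DLBCL, MCL, FL, PTCL, MF and CLL". The null rate is 5% and the one-sided level 0.05. The section closes by promising a responder rate and p-value for the same six cohorts. Its only responder definition is "Responders will be considered as subjects with 2014 Lugano Classifications given by Complete Response (CR) or Partial Response (PR", and non-responders are likewise given as Lugano categories (NR, SD or PD).

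The criteria are assigned by disease elsewhere:

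- **Lymphoma.** SAP 2.3.1.1 says the Lugano Classification is "used to determine the stage of subjects with lymphoma, and the response to treatment". Protocol 8.6.1 and footnote i of SAP Table 2 agree.
- **MF.** SAP 2.3.1.1 says the IWG-MRT and "European LeukemiaNet (ELN) response criteria will be used to evaluate the response to treatment with ASN002". It lists four endpoints: "Splenic response rate at week 24"; clinical improvement at the same week; "Symptom response evaluated using the Myeloproliferative Neoplasm Symptom Assessment Form (MPN-SAF) tool"; and the rate of red-cell transfusion. Protocol 11.1.1.3 has the same list. SAP 9.1.3 adds that "the frequency of response and type of response according to IWG-MRT response criteria for subjects with MF will be evaluated". The protocol synopsis (Efficacy Analyses) says of Part B reporting: "the overall response rate (ORR), time to progression (TTP) and progression free survival (PFS) will be reported for each lymphoma histology, MF, and CLL".
- **CLL.** SAP 2.3.1.1 and 9.1.4 use IWCLL criteria. Objective response rate is a listed endpoint, and partial response with lymphocytosis is a separate named category.

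Protocol section 15 gives the SAP priority where the two documents differ.

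**The concern.** Preliminary efficacy is part of the Part B primary objective, and this binomial test is the only hypothesis test planned for it. A programmer following SAP 9.1.1 would find no Lugano category for any MF or CLL subject. Someone must then supply a responder definition that the SAP does not contain.

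For CLL the substitute is nearly obvious. For MF it is not: the candidates are several, they are measured differently, and none is designated for the test. The study is open-label, and SAP section 12 says analyses will be run on an ongoing basis. A definition settled late could therefore be settled by people who have seen the responses.

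**Working it through.** **1. The plan's own figures.** SAP section 4 and protocol 15.1 give n=14 per cohort, null rate 0.05, rejection at 3 or more responses, type I error 0.02, and power 0.9 at a true rate of 0.4. The exact binomial tail is P(X≥r) = Σ C(14,x) p^x (1−p)^(14−x), summed over x from r to 14.

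- P(X≥3 | p=0.05) = 0.0301; stated 0.02.
- P(X≥3 | p=0.40) = 0.960; stated 0.9.

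The stated pair does not follow from the one-stage rule as written. That is a separate matter. The 3-of-14 rule does agree with the p<0.05 test in SAP 9.1.1, and nothing below uses the stated pair.

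**2. Does the written rule fit each cohort?**

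| Cohort | Criteria assigned | Lugano category available? | Responder for the test defined? |
|---|---|---|---|
| DLBCL, MCL, FL, PTCL | Lugano | Yes | Yes: CR or PR |
| CLL | IWCLL | No | Nearly: response rate is named; partial response with lymphocytosis is not placed |
| MF | IWG-MRT/ELN | No | No |

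For MF, each place that might fill the gap stops short. The endpoint lists (SAP 2.3.1.1, protocol 11.1.1.3) contain no overall response rate and designate no tested variable. SAP 9.1.3 and protocol 15.6.1.3 evaluate frequency and type of response without saying which categories count. The synopsis promises an overall response rate without defining it or tying it to the test. The sample-size sections speak only of responses.

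**3. How much one classification matters at n=14, null rate 0.05.**

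- 3 responders: P(X≥3) = 0.0301, reject.
- 2 responders: P(X≥2) = 0.153, do not reject.

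**4. Illustration of late choice in MF.** Assumptions, none from the documents: the three endpoints that can be scored per subject (splenic, clinical improvement, symptom) are the candidates; each has a true rate of 0.05; 14 subjects are analysed; the most favourable endpoint is used.

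- One pre-named endpoint, or three that coincide: 0.030.
- Two independent: 1−(1−0.0301)² = 0.059.
- Three independent: 1−(1−0.03005)³ = 0.087.
- Three positively correlated within subject (simulation, latent correlation 0.3 to 0.9): about 0.085 down to about 0.06.

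The SAP 6.5 level is one-sided 0.05.

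**5. The figure depends on the number analysed.** The primary efficacy population is per-protocol, and cohorts are analysed from 5 subjects. For three independent endpoints, with the cut-off set by p<0.05:

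| n analysed | Responders needed | One endpoint | Best of three |
|---|---|---|---|
| 5 to 7 | 2 | 0.023 to 0.044 | 0.066 to 0.127 |
| 8 to 11 | 3 | 0.006 to 0.015 | 0.017 to 0.045 |
| 12 to 13 | 3 | 0.020 to 0.025 | 0.058 to 0.072 |
| 14 | 3 | 0.030 | 0.087 |

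**6. Whether 5% suits MF.** The documents give no reason for a 5% null for any particular MF variable. If the uninteresting rate for the chosen variable were 0.05, 0.10, 0.15 or 0.20 (assumed), the chance of 3 or more of 14 at that rate would be 0.030, 0.158, 0.352 or 0.552.

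**The case against.** The best defence is that this is a missing cross-reference. SAP 9.1.1 is headed for the lymphomas. Its sentence about each binomial test speaks only of responders versus non-responders, and Lugano enters in the next sentence. SAP 9.1.3 and 9.1.4 then give MF and CLL their own criteria. A sensible analyst would not score MF by Lugano.

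That defence stands in part. A reader might infer that the sponsor means to apply Lugano to MF and CLL, making every such subject a non-responder (0 of 14, p=1.0). The sections that assign other criteria speak against that intention. The defence also largely settles CLL: response rate under IWCLL is named, and the extra category is itself called a partial response.

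It does not settle MF. Reading IWG-MRT into the test still leaves open which categories are responses and whether clinical improvement, a separate endpoint in the list, is one of them. If splenic response is meant, both palpation and MRI/CT are planned. The mention of spleen volume in SAP 9.1.3 and the week-24 scan in Table 2 point towards imaging, but neither defines a responder.

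It is also fair to say that efficacy is preliminary, and that the SAP plans no multiplicity adjustment: with independent cohorts and a null that holds in all six, the chance of at least one rejection is already 1−(1−0.0301)^6 = 0.167. That makes the consequence modest. It does not supply the missing definition.

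**Conclusion.** The point holds and should be fixed. As written, the rule does not fit two of the six tests. For MF (14 of 84 planned Part B subjects, 17%) the responder for the test is undefined. For CLL (another 14) one clarification is missing. This rests on the text alone and needs none of the illustrative figures.

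The limits are these. The tests matter only where a cohort has at least 5 subjects at the recommended Part B dose and Part B is completed for at least one indication; otherwise reporting is descriptive or by listing. The 3-versus-2 contrast is for 14 analysed subjects. The range 0.030 to 0.087 assumes three candidate endpoints at a true rate of 0.05 with n=14; its upper end needs independence, and at 8 to 11 subjects the best-of-three figure stays below 0.05.

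Three stronger readings go too far. One is that MF response is specified nowhere: IWG-MRT/ELN criteria are named, and what is missing is the cut for the test. Another is that the MF endpoint will be chosen from the data: ongoing open-label analysis makes that possible, but no passage plans it. The third is that the CLL test is seriously weakened: the documents give no share of responses that would be of the lymphocytosis type, so no loss of power can be calculated.

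**What to change.** - **SAP 9.1.1.** Limit the Lugano CR/PR versus NR/SD/PD rule to DLBCL, MCL, FL and PTCL, and point to 9.1.3 and 9.1.4 for the other two cohorts.
- **SAP 9.1.3, before further data review.** Define the MF responder for the test. Named IWG-MRT/ELN response categories are preferable, because 9.1.3 already evaluates that response; state whether clinical improvement counts. Failing that, name one listed endpoint with its time point and measurement method (for splenic response, palpation or MRI/CT). Align the choice with the overall response rate promised in the synopsis, and confirm that a 5% null suits it.
- **Alternative for MF.** Take MF out of the binomial test, report its endpoints descriptively, and record the departure from protocol 15.1 in SAP section 14, which now reports no changes.
- **SAP 9.1.4.** Define CLL responders as IWCLL CR or PR, state that partial response with lymphocytosis counts, and add a sensitivity count without it.

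The cost is a few sentences in three SAP sections, plus one in section 14 if MF leaves the test. No visit, procedure or subject is added.
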